- Agree to comply with the conduct and terms of the study specified herein and with any other study conduct procedures provided by the Sponsor, Alkahest, Inc., or their designee
- Agree to assume responsibility for the proper conduct of the study at this site, including complying with current relevant versions of the US Food and Drug Administration (FDA) regulations, the International Conference on Harmonization (ICH) GCP guidelines, the Declaration of Helsinki, and all applicable rules, regulations, and federal, state, and local laws relating to the conduct of clinical studies and the protection of human subjects.
- Agree not to implement deviations from or changes to the protocol or protocol amendments without agreement from the Sponsor and prior submission to and written approval (where required) from the Institutional Review Board (IRB) or Independent Ethics Committee (IEC), except when necessary to eliminate an immediate hazard to the subjects, or for administrative aspects of the study (where permitted by all applicable regulatory requirements).
- Agree to onsite monitoring of all source documents by Alkahest, Inc. or designee and to onsite inspection of source documents by appropriate regulatory authorities, including but not limited to the FDA, local governing regulatory bodies, and IRB inspectors.

Investigator's Signature

Date

Print Name

PROTOCOL SUMMARY

Title: A Randomized, Placebo-Controlled, Double-Blind Pilot Study to Evaluate the Effect of GRF6021 on Intracellular Signaling Cascades in Blood Leukocytes and Postoperative Recovery Following Primary Hip or Knee Arthroplasty

Précis: This is a randomized, placebo-controlled, double-blind pilot study to investigate the effects of GRF6021, a 5% human plasma protein fraction administered by intravenous (IV) infusion, on intracellular signaling cascades in blood leukocytes in subjects undergoing primary hip or knee arthroplasty.

The study will enroll approximately 45 subjects with the aim of having 40 evaluable subjects randomized in a 1:1 ratio to active treatment or placebo. Each subject will receive 4 infusions of 250 mL GRF6021 or 4 infusions of 250 mL placebo (normal saline):

- 1) 1 infusion on the day before surgery
- 2) 1 infusion on the day of surgery within 4 hours before surgery start (first incision)
- 3) 1 infusion on the day of surgery upon arrival in the postoperative care unit (within 5 hours after the first incision)
- 4) 1 infusion on the day after surgery

Each infusion will be administered over approximately 30 minutes according to Stanford Hospital procedures for colloid infusions, but infusion rates and infusion time will be adjusted according to tolerability as determined by the anesthesiologist and infusion nurse. The infusion procedure of active and placebo agents will be identical to maintain the blind. The following measures will be taken to ensure adequate blinding during infusions: blinding of subjects, study coordinators, physicians, and raters to treatment allocation; use of unblinded infusion nurses; and measures to block view of the vial and drip chamber throughout the infusion.

Mass cytometry (CyTOF), a multiplexed, high-content immune profiling technology, will be used to provide high-resolution surveillance of circulating immune cells and the response to GRF6021 infusions on surgical recovery. Additional functional and quality of life assessments will be measured at baseline and approximately twice weekly for 6 weeks after hospital discharge.

Objectives: The primary objective of the study is to investigate the effect of GRF6021 on intracellular signaling cascades in blood leukocytes as determined by CyTOF. Secondary objectives include the effect of GRF6021 on clinical recovery parameters in patients undergoing primary hip or knee arthroplasty, safety and tolerability of GRF6021, and the effects of GRF6021 on plasma proteomics.

Endpoints: **Primary Endpoint:**

- Effect of GRF6021 on intracellular signaling cascades in blood leukocytes as determined by CyTOF.

Secondary Endpoints:

- Change from baseline in 3-Minute Diagnostic Interview for Confusion Assessment Method (3D-CAM).
- Time to 50% recovery of baseline value on the Surgery Recovery Scale (SRS).
- End of study treatment comparison of the Western Ontario and McMaster Universities Osteoarthritis Index (WOMAC)
- Time to a score of < 12/40 on a subset of questions from the WOMAC, Pain Subscale.
- Time to a score of < 18/60 on a subset of questions from the WOMAC, Physical Function Subscale.
- Change from baseline in the Short Form-36 (SF-36).
- Change from baseline in the Beck Depression Inventory-II (BDI-II).
- Opioid analgesic consumption during hospital stay and after discharge to end of study.
- Time to discharge.
- Perioperative outcomes (e.g., surgery duration, anesthesia duration, post-anesthesia care unit (PACU) stay duration, American Society of Anesthesiologists (ASA) status, estimated blood loss (EBL), type and amount of intraoperative fluids administered, type and amount of intraoperative blood products, dose and type of anesthesia (general, regional), and intraoperative opioid dose).
- Change in functional status using the ActiGraph wearable device providing measurements for physical activity/function and sleep (starting at least 3 days prior to surgery and continuing until the end of the study).
- Change from baseline in clinical laboratory parameters.
- Change from baseline in vital sign measurements.
- Change from baseline in electrocardiogram (ECG).
- The effects of GRF6021 on plasma proteomics.

Population: The study will enroll approximately 45 subjects with the aim of having 40 evaluable subjects between 50 and 85 years of age undergoing primary hip or knee arthroplasty.

[figure not shown]
Phase: 2

Number of Sites: Single site pilot study (Stanford University)

Description of Study Agent: GRF6021: A 5% human plasma protein fraction for IV infusion

Study Duration: Approximately 12 months

SCHEMATIC OF STUDY DESIGN

1.2 STUDY ORGANIZATION

The name and contact information of the responsible party and individuals involved with the study (e.g., investigator(s), Sponsor's medical expert and study monitor, Sponsor's representative(s), laboratories, steering committees, and oversight committees (including Independent Ethics Committees (IECs) and Institutional Review Boards (IRBs), as applicable) will be maintained by the Sponsor, or their designee, and provided to the investigator.

2 INTRODUCTION

2.1 BACKGROUND INFORMATION

Total knee arthroplasty (TKA) and total hip arthroplasty (THA) are effective treatments for end-stage osteoarthritis that significantly improve pain, mobility, function, and quality of life for most people who undergo them in both the short- and long-term (Mayer 2017, Martinez-Cano 2017). Given their success and the aging population, there has been a rise in the number of hip and knee arthroplasties performed in the US. By 2030, a study projects an estimated growth of 174% and 673% in the primary total hip and knee arthroplasties respectively (Kurtz 2007). Because TKA and THA are elective procedures, quality of life outcomes, including

physical, psychological, and social factors, inclusive of the return to normal activities, are important considerations (Martinez-Cano 2017, Fragiadakis 2015).

Convalescence after surgery is highly variable with inter-individual variability in fatigue, pain, and functional impairment (Gaudillière 2014, Kehlet 2003). Past studies have explored the association of preoperative psychological status with outcomes of total joint replacement surgery (Lingard 2007, Judge 2012, Faller 2003, Ayers 2004), and additional studies have demonstrated pain catastrophizing or negative preoperative emotional state is responsible for poor outcomes with resultant delays in recovery (Witvrouw 2009, Edwards 2008). In addition to psychological variables, physiological factors also play a vital role in determining duration of recovery. The physiologic stress response, characterized by endocrine and neuroimmune mechanisms, may also influence arthroplasty outcomes. Psychological stressors can elicit neuroimmune responses mimicking those initiated by physical trauma and/or inflammation (Deak 2017). Due to these factors, researchers have gained renewed interest in unravelling immune mechanisms in response to trauma that determine postoperative recovery (Gaudillière 2014, Fragiadakis 2015).

Surgical trauma triggers an intricate programmed immune response (Stoecklein 2012). Characteristics of this injury-mediated series of intracellular signaling cascades are associated with recovery from surgery. Specifically, changes in cyclic AMP-responsive element-binding protein 1 (CREB), signal transducer and activator of transcription 3 (STAT3), and nuclear factor kappa-light-chain-enhancer of activated B cells (NF- κ B) signaling in monocytes were associated with postoperative functional hip recovery, fatigue, and pain, respectively (Gaudilliere 2014). Therefore, measuring the effect of GRF6021 on intracellular phosphorylation events in precisely phenotyped immune-cell subsets may increase our understanding of the immunomodulatory effects of GRF6021 and its potential to enhance postoperative recovery.

In 2011, data in parabiotic animal models suggested that differences in systemic chemokines, immune signaling molecules, and rejuvenating factors between young and old animals may explain the benefits in old animals of heterochronic parabiosis (Villeda 2011). Following these findings, the investigators performed a study to explore the therapeutic effects of systemic exposure of aged mice to young mouse plasma by intravenous injection (Villeda 2014). Systemic administration of young mouse plasma into aged mice improved age-related impairments.

Results from nonclinical studies conducted by Alkahest (see Section 2.2, Rationale) have repeatedly demonstrated beneficial effect of the plasma protein fraction GRF6021 in age-related decline and histopathological endpoints in mouse models, including a reduction in neuroinflammation. Specifically, treatment with GRF6021 – in aged mice and in mouse models characterized by neuroinflammation – reduces the number of microglia labeled with either ionized calcium binding adaptor molecule 1 (Iba1) or cluster of differentiation 68 (CD68). Since microglia derive from the same monocytic lineage as blood monocytes and tissue macrophages, these data demonstrate that GRF6021 has a specific effect on cells of the monocytic lineage. Given this, testing the effect of GRF6021 on intracellular signaling events in monocytes in the context of THA or TKA will provide important information about whether GRF6021 has the potential to improve postoperative recovery in patients undergoing hip and knee arthroplasty.

2.2 RATIONALE

Protocol AKST6021-211 will evaluate GRF6021 administered via intravenous (IV) infusion. GRF6021 is a purified 5% plasma protein fraction depleted of coagulation factors and gamma globulins that is manufactured by fractionation from pooled human plasma by Grifols Therapeutics, Inc. Additional processing steps with high pathogen clearance capacity are undertaken to reduce the potential for pathogen transmission. GRF6021 is

indicated for the treatment of hypovolemic shock due to burns, crushing injuries, abdominal emergencies, and any other condition where there is a predominant loss of plasma fluids. GRF6021 is also used more generally as a colloid for volume expansion. Fluid management is an essential part of surgical care as both inadequate and excessive fluid replacement can increase the stress on the circulatory system with deleterious consequences for tissue healing and recovery after surgery. Intraoperative and postoperative fluid management can involve crystalloids, colloids, or a combination thereof. Crystalloids (e.g. normal saline) are associated with interstitial and pulmonary edema, because up to 80% of the fluid volume can distribute to the interstitial (extravascular) space. Colloids (e.g. 5% albumin or 5% plasma protein fraction) provide better volume expansion with less interstitial edema; however, they are associated with potential hypersensitivity reactions ([Kayilioglu 2015](#)). There is controversy in the field as to which type of fluid replacement is more appropriate, and clinical care often depends on the preferences of the individual anesthesiologist and surgeon. Therefore, the use of either crystalloids and/or colloids (like GRF6021) is part of the intraoperative and postoperative standard of care in US hospitals.

Nonclinical studies conducted by Alkahest have demonstrated that GRF6021 confers beneficial outcomes in cognitive decline, motor function, neuroinflammation, pain, and histopathological endpoints in mouse models ([ALK-2015-R002](#), [VIV-2016-R003](#), [VIV-2016-R009](#), [VIV-2016-R014](#), [VIV-2016-R020](#), [VIV-2016-R021](#), [VIV-2016-R024](#), [VIV-2017-R025](#), [VIV-2017-R036](#), [VIV-2017-R038](#), [VIV-2018-R069](#), [2018-CET01](#), [VIV-89](#)).

Surgical trauma triggers an intricate programmed immune response ([Stoecklein 2012](#)). Characterization of this injury-mediated series of intracellular signaling cascades can provide insights about time to, and ease of, recovery from surgery. Therefore, measuring immune function responses at the single-cell level, and functional and phenotypic characterization of signals specific to immune cell subsets, may point to diagnostic signatures and potential therapeutic targets that could postoperatively improve patient recovery ([Gaudillière 2014](#), [Fragiadakis 2015](#)).

In this randomized, placebo-controlled pilot study, approximately 45 patients will be enrolled (with the goal of obtaining 40 evaluable subjects) who are scheduled to undergo primary hip or knee arthroplasty without major comorbidities. Subjects will be randomized 1:1 (active: placebo) to evaluate the effect of GRF6021 on intracellular signaling cascades in blood leukocytes and the relationship of these immunomodulatory effects with postoperative recovery. In addition, the effects of GRF6021 on plasma proteomics will be investigated. Four (4) doses of 250 mL of GRF6021 or placebo will be administered over 3 days. Each dose will be administered over approximately 30 minutes as per Stanford Hospital standard procedures, but infusion rates and infusion time may be adjusted according to tolerability or other factors as determined clinically by the anesthesiologist and infusion nurse. Assessments of surgical recovery will be measured at baseline, during the inpatient stay, and for 6 weeks after hospital discharge.

Human dose levels were selected to be consistent with the standard clinical use of GRF6021 as a colloid. In previous studies of patients undergoing THA at Stanford, the median volume of crystalloids for fluid management was 1,500 mL (interquartile range 1,000 to 2,000 mL) ([Gaudilliere 2014](#)). Given a conversion factor of 1.5-2 between colloids and crystalloids, 1,500 mL of crystalloid is the equivalent of 750-1,000 mL of colloid. The total volume of GRF6021 that will be administered in this study is 1,000 mL.

In mice, no safety concerns were observed using repeated daily (5-7) doses of 150 μ L, which is the dosing regimen that produced robust anti-neuroinflammatory effects. Because GRF6021 contains a complex mixture of proteins with a molecular weight predominantly <100 kDa, and because the beneficial effects of these proteins on inflammation are believed to occur in the circulation, the concentration of these proteins per blood volume appears to be the scaling method most likely to accurately estimate the human potential effective dose.

Using isometric scaling based on blood volume, the mouse dose of 150 μ L is equivalent to a human dose of 413 mL, as outlined in **Table 1**. The dose proposed in this study is 250 mL GRF6021 per infusion.

Table 1 Isometric Scaling Based on Blood Volume

	Mouse	Human Equivalent Dose (70 kg person)	Human Proposed Dose
GRF6021 Protein Content	5%	5%	5%
Dose Volume	150 μ L	413 mL	250 mL
Protein per Dose	7.5 mg	20.7 g	12.5 g
Blood Volume	2 mL	5,500 mL	5,500 mL
Protein per Dose per mL of Blood	3.75 mg/mL	3.75 mg/mL	2.3 mg/mL

Given the long-standing clinical experience with GRF6021 in which doses of 250 mL to 1.5 L have been well tolerated, and the standard-of-care use of GRF6021 and similar colloids for fluid management, the investigational regimen of 4 doses of 250 mL of GRF6021 over a period of 3 days represents a reasonable and appropriate dosing regimen for evaluation in this clinical context ([PSUR](#), [PI](#), [Bertrand 1959](#), [Gahart 2019](#)).

2.3 POTENTIAL RISKS AND BENEFITS

2.3.1 KNOWN POTENTIAL RISKS

GRF6021, a 5% human plasma protein fraction, is reduced in coagulation factors and gamma globulins and serves as a viable source of soluble, infusible plasma proteins from healthy male and female donors.

GRF6021 has been marketed since 1958 in the US, is approved in other parts of the world, and has a well-established safety profile with a very low frequency of reported infusion reactions (0.002%) ([PSUR](#)). Based on the cumulative review of post-marketing safety surveillance data ([PSUR](#)), the benefit-risk balance for GRF6021 as an investigative product in individuals undergoing THA or TKA is favorable. Because it has been depleted of the majority of immunogenic proteins, GRF6021 is not expected to alter the blood typing characteristics of the recipient and should not sensitize humans to its subsequent administration ([Bertrand 1959](#)). ABO antigen typing is not required prior to administration. Finally, the additional steps taken during production to remove viral pathogens provide an increased margin of pathogen safety in comparison to fresh frozen plasma.

GRF6021 is not expected to significantly alter safety laboratory parameters, including urinalysis, coagulation times, prothrombin times, prothrombin consumption, platelet counts, or fibrinogen levels when given in quantities of up to 1000 mL ([Bertrand 1959](#)). Hypotension may occur, particularly following rapid infusion. The blood pressure may normalize spontaneously after the slowing or discontinuation of the infusion. Vasopressors will also correct the hypotension ([PI](#)). GRF6021 is contraindicated for use in patients on cardiopulmonary bypass as severe hypotension has been reported ([Bland 1973](#)). GRF6021 is contraindicated in patients with severe anemia, congestive heart failure, or increased blood volume ([PI](#)).

GRF6021 is made from human plasma and may carry a risk of transmitting infectious agents, e.g., viruses, the variant Creutzfeldt-Jakob disease (vCJD) agent, and, theoretically, the Creutzfeldt-Jakob disease (CJD) agent. The risk that GRF6021 can transmit an infectious agent has been reduced by screening plasma donors for prior exposure, testing donated plasma, and including manufacturing steps with the capacity to inactivate and/or remove pathogens.

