5.2 EXCLUSION CRITERIA

An individual will not be eligible for inclusion if any of the following criteria apply:

1. Blood coagulation disorders, including severe liver disease, vitamin K deficiency, von Willebrand disease, hemophilia A or B or other known deficiencies in clotting factors (fibrinogen, prothrombin, factor VII, X, XI, XII, or XIII) that in the opinion of the investigator could put the subject at risk.
2. Subjects who started chronic anticoagulant therapy (warfarin, heparin, low-molecular weight heparin, or Factor Xa inhibitors) in the last 6 months. Use of pre-, intra- and post-operative anticoagulation according to standard of care is permitted. Use of antiplatelet drugs (e.g., aspirin or clopidogrel) is permitted.
3. History of a known hypercoagulable state, including Factor V Leiden thrombophilia, prothrombin gene mutation, deficiencies in antithrombin, protein C or protein S, elevated levels of fibrinogen, or dysfibrinogenemia.
4. History of deep vein thrombosis or pulmonary embolism in the last 6 months and/or if it is associated with a known hypercoagulability disorder.
5. History of disseminated intravascular coagulation, thrombotic thrombocytopenic purpura, or heparin-induced thrombocytopenia in the last 5 years.
6. Prior hypersensitivity reaction to any human blood product including plasma or a plasma protein fraction.
7. Treatment with any human blood product, including transfusions and IV immunoglobulin, during the 6 months prior to screening.
8. History of immunoglobulin A (IgA) or haptoglobin deficiency; at screening a test for IgA must be performed to confirm detectable levels of IgA.
9. History of complications of IV immunoglobulins, including stroke, anaphylaxis, or thromboembolic events.
10. History of major surgery, trauma, or injury in the last 3 months or minor surgery in the last 1 month.
11. History of unstable coronary heart disease (e.g. myocardial infarction or severe or unstable angina in the 6 months prior to dosing).
12. Moderate or severe congestive heart failure (New York Heart Association Class III or IV or metabolic equivalent < 4).
13. Uncontrolled high blood pressure (systolic blood pressure of 170 mmHg or higher and/or diastolic blood pressure of 110 mmHg or higher) despite adequate treatment during the 3 months prior to dosing.
14. Current treatment with 4 or more antihypertensive medications of different classes.

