15. Clinically significant abnormalities on screening electrocardiogram (ECG) that in the opinion of the investigator could put the subject at risk, including QTc intervals (using Fridericia's correction formula) of ≥ 450 ms in men and ≥ 470 ms in women.
16. Current, active liver disease: > 3-fold elevation of liver enzymes (alanine aminotransferase (ALT)

- and aspartate aminotransferase (AST) over upper limit of normal.
17. Clinically significant abnormalities in complete blood count (CBC), complete metabolic panel, serum albumin, or coagulation.
 18. History of a major infection (e.g. bacterial pneumonia) in the last 3 months, or recent minor infection (e.g. influenza, urinary tract infection) or fever (measured body temperature above 100.5 degrees F on 2 consecutive days) that in the assessment of the Principal Investigator could interfere with the primary endpoint.
 19. Severe anemia (hemoglobin < 8 g/dL).
 20. Urine protein-to-creatinine ratio (UPCR) of > 1.5 grams of protein per gram of creatinine.
 21. Inadequate venous access to allow IV drug delivery or multiple blood draws.
 22. Concurrent participation in any other therapeutic treatment trial. If there was prior clinical trial participation, subject must have discontinued investigational agents for at least 30 days for small molecules, and 1 year for active or passive immunotherapies prior to screening.
 23. Current diseases associated with significant alterations in immune function, including, but not limited to, autoimmune disease and cancer, except adequately-treated squamous or basal-cell carcinoma.
 24. Ongoing immunosuppressant treatment or within 5 half-lives of the treatment.
 25. History of substance abuse (alcohol, drugs of abuse) in the last 2 years.
 26. Functional impairment of major joint or lower extremity other than joint undergoing surgery.
 27. Any other condition and/or situation that the investigator believes may interfere with the safety of the subject, study conduct, or interpretation of study data.

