7.1.1.1.5 Physical Examination

A physical examination will be performed to assess the following organ systems: lungs/chest, heart, abdomen, neuro/spine. Height and weight will also be measured at screening. Should the subject have a physical exam, including height and weight measurements, as part of standard of care during the screening window, then the results may be obtained from the subject's medical record for the purposes of assessing eligibility.

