Section 5.2	Removed: Exclusion Criteria #14 History of Torsades de Pointes dysrhythmia.	GRF6021 is not associated with any known effects on ECG or electrolytes or any cardiac risk. Thus, The PI should use his/her clinical judgement to determine whether an ECG abnormality would warrant the exclusion of the subject.
Section 5.2	Previously read: Exclusion Criteria #15 Clinically significant abnormalities on screening electrocardiogram (ECG) including QTc intervals (using Fridericia's	GRF6021 is not associated with any known effects on ECG or electrolytes or any cardiac risk.

	
correction formula) of ≥ 450 ms in men and ≥ 470 ms in women.
 
Now reads: Exclusion Criteria #15 Clinically significant abnormalities on screening electrocardiogram (ECG) that in the opinion of the investigator could put the subject at risk, including QTc intervals (using Fridericia's correction formula) of ≥ 450 ms in men and ≥ 470 ms in women.
	Thus, The PI should use his/her clinical judgement to determine whether an ECG abnormality would warrant the exclusion of the subject.
Section 5.2	
Previously read: Exclusion Criteria #19 History of a major infection (e.g. bacterial pneumonia) in the last 3 months, or minor infection (e.g. influenza, urinary tract infection) or fever (measured body temperature above 100.5 degrees F on 2 consecutive days) in the last 1 month.
 
Now reads: Exclusion Criteria #18 History of a major infection (e.g. bacterial pneumonia) in the last 3 months, or recent minor infection (e.g. influenza, urinary tract infection) or fever (measured body temperature above 100.5 degrees F on 2 consecutive days) that in the assessment of the Principal Investigator could interfere with the primary endpoint.
	The PI should use his/her clinical judgment to determine whether the infectious or inflammatory process was systemic, in which case there may be effects on the primary endpoints.
Section 5.2	
Previously read: Exclusion Criteria #20 Hemoglobin < 9 g/dL in women and < 10 g/dL in men.
 
Now reads: Exclusion Criteria #19 Severe anemia (hemoglobin < 8 g/dL).
	GRF6021 is contraindicated in severe anemia because of the risk of hemodilution; however, there is no known risk in mild or moderate anemia.

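### Section 2.3.1 lists heart failure (no severity limit) and increased blood volume as contraindications, but exclusion 12 bars only moderate or severe heart failure and no entry criterion names increased blood volume

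*Protocol*

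**What the plan says.** Protocol Section 2.3.1, with the prescribing information as its source, gives three contraindications in one sentence: "GRF6021 is contraindicated in patients with severe anemia, congestive heart failure, or increased blood volume".

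Section 5.2 takes up two of them by name:

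- Exclusion 12: "Moderate or severe congestive heart failure (New York Heart Association Class III or IV or metabolic equivalent < 4".
- Exclusion 19: "Severe anemia (hemoglobin < 8 g/dL".

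It closes with a discretionary criterion, exclusion 27, whose opening part reads "Any other condition and/or situation that the investigator believes may interfere with the safety of the subject".

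Section 2.2 describes the intended population as patients having "primary hip or knee arthroplasty without major comorbidities". It sets the exposure at four infusions of 250 mL over three days and presents GRF6021 as a colloid used for volume expansion. On fluid management it warns that "both inadequate and excessive fluid replacement can increase the stress on the circulatory system".

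For the screening exam, Section 7.1.1.1.5 says: "A physical examination will be performed to assess the following organ systems: lungs/chest, heart, abdomen, neuro/spine". Sections 7.1.1.2.5 and 7.3.4 schedule a targeted exam before the Day 1 infusion that covers heart, lungs and peripheral edema.

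**The concern.** Entry criteria are where a protocol turns a known contraindication into a rule that every screener must apply. Here the safety section and the criteria disagree. A subject with NYHA class I or II heart failure and a metabolic equivalent of 4 or more falls within the contraindication as Section 2.3.1 words it, yet meets no exclusion that names heart failure. A subject with increased blood volume meets no exclusion that names that condition at all.

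The stake is patient safety. In the active arm such a subject would be due 4 × 250 = 1,000 mL of a volume-expanding colloid. The first 250 mL is given the day before surgery, ahead of any surgical fluid loss, and the subject then goes home until the next morning. Section 2.3.2 acknowledges no known benefit in this population, so nothing stated in the protocol offsets exposing a contraindicated subject. Section 2.3.1 calls benefit-risk favorable in hip and knee arthroplasty, and Section 2.2 reports that 250 mL to 1.5 L has been well tolerated. Neither statement addresses patients with heart failure or increased blood volume.

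**Working it through.** The protocol gives no figure to reproduce. The check is a comparison of Section 2.3.1 with all 6 inclusion criteria (Section 5.1) and all 27 exclusion criteria (Section 5.2): 6 + 27 = 33.

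| Contraindication in 2.3.1 | Criterion that names it | Coverage |
|---|---|---|
| Severe anemia | Exclusion 19, hemoglobin below 8 g/dL | Matched |
| Congestive heart failure, no severity stated | Exclusion 12, NYHA III or IV or metabolic equivalent below 4 | Partial: 2 of 4 NYHA classes, plus the functional-capacity limb |
| Increased blood volume | None | 0 of 33 |

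**Could "severe" govern the whole list?** It cannot sensibly qualify increased blood volume. If it were stretched to heart failure, exclusion 12 would cover that item, but increased blood volume would still have no criterion. At most this reading removes half of the point.

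**What else narrows the group?** Several criteria remove some subjects at risk of overload:

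- inclusion 3: eGFR of at least 45
- exclusions 1 and 16: severe or active liver disease
- exclusion 11: unstable coronary disease
- exclusions 13 and 14: uncontrolled blood pressure; four or more antihypertensive classes
- exclusion 15: ECG abnormalities
- exclusion 17: clinically significant abnormalities in metabolic panel or albumin
- exclusion 20: proteinuria

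None of these names heart failure or volume status, so a subject can satisfy all of them and still have either condition.

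**What is left?** For such a subject the only remaining bar is exclusion 27, which depends on the investigator judging that the condition threatens safety. The population description in Section 2.2 is not a criterion. The Day 1 exam looks for edema, but the protocol does not link its result to eligibility.

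**The case against.** The strongest reply is that exclusion 27 is itself an entry rule and the contraindication is printed in the same protocol. For such a subject to enter, the investigator would have to judge the contraindication no safety concern. This stands. A reader might infer that the criteria simply let contraindicated subjects in, but the documents show only the lack of a named criterion behind that judgment. The infusion rate and time may also be adjusted for tolerability, although that does not cap the total volume.

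It is also fair that Section 2.3.1 is a one-line summary of a source not available here. The documents show two sections in disagreement; they do not show which is wrong. The wording of exclusion 12 may be a deliberate threshold, in which case what is missing is its reason.

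Three stronger readings are tempting and not supported:

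- **That the revision history shows an oversight.** Section 18.1 explains the anemia limit: "GRF6021 is contraindicated in severe anemia because of the risk of hemodilution; however, there is no known risk in mild or moderate anemia". It says nothing similar about heart failure. But a change log explains changes, and a criterion that did not change would not appear there.
- **That no rule exists for holding a dose in an overloaded subject.** Section 6.1.5 refers to an Infusion Administration Manual that is not among the documents and may contain one.
- **That subjects could be randomized before eligibility is settled.** Section 7.3.3 places randomization after eligibility is confirmed, and SAP Section 7.6 says the same.

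**Conclusion.** The point holds as an internal inconsistency with a safety consequence. Of three stated contraindications, one has a matching exclusion, one is covered in part and one is not named in any of the 33 criteria. For NYHA class I or II heart failure with metabolic equivalent of 4 or more, and for increased blood volume, protection rests on the investigator's judgment once the other criteria are met.

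The conclusion assumes that Section 2.3.1 means heart failure of any severity, which is its plain reading; the increased-blood-volume half does not depend on this. The number of subjects affected is unknown, because the documents give no prevalence, and it may be small in an elective population. Nothing in the documents shows that a contraindicated subject was enrolled or harmed.

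SAP Section 7.3 reports that enrollment ended with 37 evaluable subjects. New wording therefore cannot alter who was dosed in this trial. Its value is in correcting the protocol and any later study that reuses these criteria. On that footing it should be fixed.

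**What to change.** 1. **Exclusion 12.** Change it to: *Congestive heart failure (any NYHA class).* Metabolic equivalent below 4 should not become a stand-alone exclusion. In the current text it sits in parentheses as part of the definition of moderate or severe heart failure; on its own it could bar arthroplasty candidates whose capacity is limited by the joint. If class I or II is meant to be eligible, keep exclusion 12 and state in Section 2.3.1 why that is acceptable despite the contraindication.
2. **New exclusion.** Add: *Clinical evidence of increased blood volume (hypervolemia) in the investigator's judgment.* Assess it at the existing screening exam and again at the Day 1 targeted exam before the first infusion. Peripheral edema should count as one supporting sign and not as an exclusion by itself: it reflects interstitial fluid, may have other causes, and is a poor proxy for intravascular volume.

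The cost is one reworded criterion, or a sentence of justification, and one added criterion, with no new visit or exam. The eligible pool shrinks slightly, by an unknown amount. An occasional subject would fail screening late, the day before surgery. Judging hypervolemia remains clinical, but naming it means that it has to be considered for every subject.
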